6.3 Social Harms Monitoring and Reporting Requirements

Adverse social events, "social harms" will be monitored closely throughout the study. At each follow-up visit, a series of structured questions will be used to probe for interpersonal, legal, housing and healthcare problems that have occurred as a result of study participation. All subjects will also be reminded of the importance of reporting problems to study staff between regularly scheduled visits and instructed on how to contact study staff should problems occur during intervals between visits. Additionally, social harms reported by anyone other than study participants, e.g., family or staff members, will also be monitored and documented in site source records. When these events are serious, including incarceration, physical abuse, suicidal behavior, or homicidal behavior, they will be reported on case report forms. Whenever problems are identified, additional data regarding the severity and resolution will be described and recorded on a case report form and will include a description of actions taken by the participant, the site staff, and others to resolve or respond to the problem. The nature and frequency of these social impact reports will be monitored by the PSRT as they occur. In addition, the DAIDS DSMB will routinely review these data.

Given the status of illegal drug use, the associated social stigma and perceptions of drug users held by many members of the communities in which the study will be conducted, social harms could occur purely as a result of participation in a study targeting drug users. These could include discriminatory treatment and violence associated with possible disclosure of participants' drug or sex-related behaviors or of their HIV serostatus.

Prior to site activation, a review of local and national policies and practice affecting injection drug users will be conducted. The purpose of this review will be to verify that law, policies and enforcement strategies do not place participants in the research at significantly elevated risk of arrest, incarceration, physical harm, unwanted disclosure of drug use, or loss of access to health care relative to injection drug users not participating in the research.

The assessment will consist of two components. The first component will review and analyze the law relevant to injection drug use by examining laws concerning drug control, drug use, access to health care and privacy of medical information in each study country. This review will identify and collate constitutions and any treaties that have the force of law, statutes passed by the national, regional or local legislature, administrative regulations with the force of law and relevant court decisions interpreting these laws or regulations. This review will be conducted with the close involvement of independent legal experts in each study country.

The second component will assess how these laws are put into practice and what possible influence they have on the risks and benefits of IDU participation in the study. Qualitative data regarding the effects of law on IDUs will be gathered, along with data on stigma, social risk, and social attitudes as they apply to IDUs. These data will be collected via interviews with key informants in the legal and public health fields as well as current and former injection drug users. Data will be collected via standardized interview forms by independent researchers at each site.

The review will provide a narrative summary and analysis of the law and its likely effects on study participants. As these laws, policies and practice strategies can be expected to change over time, this review will be updated on an annual basis for the duration of HPTN 058.

To the extent possible, activities involving participants will be conducted in venues that mask the criteria for study participation. It is impossible and unwise to think that the primary purpose of the study can be kept secret (i.e., a prevention study for IDUs) from the community, including the police. An appropriate working relationship with the local law enforcement agency at each site, which recognizes the urgent need to prevent HIV in this population, has been established. Such relationships have assisted outreach staff whose presence in the community is understood and respected. Site staff do not disclose the names of participants to anyone other than members of the field research staff and have strict policies regarding the situations in which discussions of participants can take place, such as staff meetings on topics of recruitment and follow-up. All interview and laboratory data are securely stored in a confidential manner.

7.0 STATISTICAL CONSIDERATIONS

7.1 Study Design

The primary objective is to determine whether 52 weeks of substitution BUP/NX and counseling treatment in opiate addicted participants will achieve a long term (104 weeks) reduction in cumulative HIV incidence and death compared to short-term detoxification and counseling.

The study will be a phase III, multi-site, two-arm, randomized trial. In an initial safety phase, the first 50 study participants at each site will undergo randomization and in their first month receive more intensive monitoring, before reverting to the standard study monitoring schedule. These first 50 participants will therefore contribute to the full study analysis. A total of 1500 HIV-uninfected opiate dependent injectors who agree to participate in this Phase III study will be randomized to one of two study arms as outlined below in a ratio of 1:1.

Study Arm	Intervention
Substitution Arm n=750	 Sublingual BUP/NX daily up to three weeks (until dose stabilization) and then three times per week for 52 weeks; plus Weekly individual drug- and risk-reduction counseling for 12 weeks, followed thereafter by monthly counseling sessions every 4 weeks through week 52.
Detoxification Arm n=750	 Short-term detoxification with sublingual BUP/NX for 18 days maximum with a second detoxification possible at six months; plus Weekly individual drug- and risk-reduction counseling for 12 weeks, followed thereafter by monthly counseling sessions every 4 weeks through week 52.

Behavioral and serologic assessments will take place at baseline and at six-month intervals throughout the study period.

7.2 Endpoints

Ascertainment of HIV endpoints will follow a standard testing algorithm (Appendix II-B). Other endpoints are gathered via urine tests, structured interviews and questionnaires, and from external sources such as death certificates or other documentation of death, including certified letters from family members.

7.2.1 Primary Endpoint

HIV-1 infection or death by the 104 week visit

7.2.2 Secondary Endpoints

Consistent with the secondary study objectives, the following endpoint(s) will be assessed:

- 1. HIV-1 infection every six months at scheduled study follow-up visits
- 2. Mortality
- 3. Continued opiate use as measured by self-report and urinalysis
- 4. Self reported frequency of injection
- 5. Self reported frequency of injection with previously used injection equipment (needles, syringes, cookers, cottons, and rinse water).
- 6. Self-reported frequency of unprotected sex or sex sold/traded for drugs

7.3 Evaluation of Safety Phase

In a cohort of size 50, the following table presents the probabilities that 1 or more, 3 or more, 5 or more, or 10 or more subjects will experience adverse events at different underlying (true) event rates. For example, if the underlying rate of an adverse event is 10%, then there is a 57% chance that an event rate of 10% or higher will be observed (5 or more events). Likewise, if the true adverse event rate is 30% and 20% is the maximum acceptable adverse event rate for the intervention, there is a 4% (1 – 0.96) chance that there would be an inadequate number of events to conclude that the intervention has an unacceptable level of harm.

True Event	P(1 or more events,	P(3 or more events,	P(5 or more events,	P(10 or more events,
rate	n=50)	n=50)	n=50)	n=50)
1%	0.39	0.01	0.00	0.00
2%	0.64	0.08	0.00	0.00
5%	0.92	0.46	0.10	0.00
10%	0.99	0.89	0.57	0.03
20%	1.00	1.00	0.98	0.56
30%	1.00	1.00	1.00	0.96

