2.3 Study Design

This is a phase III, multi-site, two-arm, randomized, controlled trial to be conducted at a minimum in China and Thailand. An initial safety and feasibility phase will include the first 50 study participants at each site. Eligible HIV-uninfected opiate dependent injectors who agree to participate in the study and provide written informed consent will be randomized to one of two study arms in a ratio of 1:1. The two study arms are:

- "Substitution Treatment" Arm sublingual BUP/NX administered daily up to three weeks (until dose stabilization) and then three times per week for 52 weeks in addition to weekly drug- and risk-reduction counseling for twelve weeks followed by monthly counseling sessions every four weeks through week 52;
- "Detoxification Treatment" Arm short-term BUP/NX detoxification for 18 days maximum in addition to weekly drug- and risk-reduction counseling alone for twelve weeks followed by monthly counseling sessions every four weeks through week 52. The detoxification regimen may be repeated at the 26 week visit if the participant meets the same criteria for opiate dependence as at screening and has no contraindications for short-term study drug use. Women who receive a second detoxification will have another pregnancy test on the day of the first treatment dose and approximately four weeks later.

The total duration of the study will be approximately four and a half years. The initial safety and feasibility phase will take approximately 30 weeks. The accrual period in the full study will be approximately 104 weeks following the safety and feasibility phase. Participants will be followed for a minimum of 104 weeks and a maximum of 156 weeks, depending on when they are enrolled. Behavioral and serologic assessments will take place at baseline and at 26 week intervals throughout the follow-up period.

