2.3.1 Safety and Feasibility Phase

The study will begin with a safety phase during which each site will enroll 50 participants over a period of approximately six months. The primary purpose of this initial phase is to collect detailed safety data that will be made available to the sponsor and the appropriate oversight and regulatory authorities in Thailand, China, and the US, as needed. In addition, the feasibility and acceptability data on the first 50 participants in the study at each site will allow the sites to carefully plan for and establish appropriate full study operations, including procedures for study drug administration and monitoring.

The safety and feasibility phase will follow the same design as the full study, including 1:1 randomization, study drug administration, and counseling, but it will include a more intensive evaluation schedule for the first four weeks of an individual's participation in the study. For this initial phase, potential volunteers will be asked to sign a separate informed consent form that explains the additional evaluation requirements during the first four weeks of the study.

Evaluation of the initial safety and feasibility phase data will occur in two stages. The first stage will be site-specific (with available data from the two China sites likely combined) to be conducted after the 50th participant enrolled at each site completes four weeks of follow-up. The second stage will include data from all 150 safety and feasibility phase participants, in addition to other safety data accumulated up to that point, across all sites once the last participant enrolled completes four weeks of follow-up. The Statistical and Data Management Center (SDMC) will prepare comprehensive data summaries for each of the site-specific evaluations and the blinded interim evaluation for review by the Protocol Safety Review Team (PSRT) and at least one representative of the HPTN Study Monitoring Committee (SMC). The reviews will focus on both clinical and laboratory safety data and trial feasibility indicators such as screening, accrual, retention, and adherence to and acceptability of the study drug and

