2.3.2 Assessments during the Safety and Feasibility Phase

Participants in the safety and feasibility phase will follow all procedures and undergo all assessments as specified for the full study in Section 5.0. In addition, after enrollment, the clinical and laboratory evaluations listed below will be conducted every week for the first four weeks for participants in both study arms. Evaluation of participants in the detoxification arm will allow for comparison with those in the substitution treatment arm and will minimize differences in contact and attention between the two groups.

The following assessments will be employed:

- Interim medical history
- Symptom-directed physical exam
- Hemotology (Complete Blood Count [CBC] and platelet count)
- Blood chemistry (creatinine)
- Liver function tests (ALT, bilirubin)
- Urine tests for drug use
- Assessment of social harms
- Acceptability assessment at week 4

Management, reporting and review of adverse events and social harms will follow the procedures specified for the full study in Section 6.0.

Each participant will complete an intervention acceptability assessment at the completion of the fourth week of the study. Study staff not involved in delivery of the counseling or drug intervention components will administer these assessments.

Adherence to the intervention components will be measured by participants' completion of the individual counseling sessions and drug dispensing visits as scheduled during the first four weeks of the study.

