Specifically, the 'standard' level of reporting defined in the DAIDS EAE manual will be followed for the first 52 weeks of follow-up for participants in both study arms (from study enrollment until the participant completes 52 weeks of follow-up or is terminated from study participation for any reason). Conditions and illnesses identified in participants prior to randomization will be considered pre-existing conditions and will not be reported as adverse events, unless the condition worsens after randomization (increases in severity or frequency), in which case it would be reported as an AE.

The study drug in HPTN 058 is the BUP/NX combination (Suboxone), provided for 52 weeks to participants randomized to the substitution arm and, for participants randomized to the detoxification arm, up to 18 days beginning at randomization and/or within 30 days of the six month visit; therefore it is the relationship of all AEs to this product that is to be considered in determining the reporting requirements for each AE (e.g., whether the AE must be reported in an expedited manner to DAIDS).

All adverse events occurring in participants through week 52 will be graded according to the DAIDS Table for Grading the Severity of Adult and Pediatric Adverse Events, dated December 2004, which will be included in the SSP Manual and is available at the following website: http://rcc.tech-res-intl.com. All serious adverse events (SAEs), regardless of severity or relatedness, and all AEs that otherwise meet the criteria for expedited reporting to DAIDS (EAEs) occurring to participants in either study arm through week 52 will be reported on a standard AE DataFax case report form for entry into the study database. AEs that are not serious or do not otherwise meet the criteria for expedited reporting to DAIDS will be recorded in the study source documentation but will not be included in the study database. As noted above, for the purposes of this study, outpatient or inpatient hospital/medical facility admission for drug addiction treatment or rehabilitation will not be considered a serious adverse event.

There will be no active reporting of adverse events after the period specified above (52 weeks of follow-up); however, unexpected, serious adverse drug reactions must be reported if the study site staff become aware of the events on a passive basis, i.e., from publicly available information.

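### The 4% miss rate in Section 7.3 holds only for an event equally common in both arms that reaches the review, and common clinical adverse events are kept out of the database

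*Protocol*

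**What the plan says.** Section 7.3 opens its calculation thus: "In a cohort of size 50, the following table presents the probabilities that 1 or more, 3 or more, 5 or more". The last column covers counts of at least 10, and the true rates run from 1% to 30%. The section then reads the table as a check on the treatment: "if the true adverse event rate is 30% and 20% is the maximum acceptable adverse event rate for the intervention, there is a 4" per cent miss rate, which is one minus the 0.96 in the table. It describes this miss as the "chance that there would be an inadequate number of events to conclude that the intervention has an unacceptable level of harm". No arm and no type of adverse event is named.

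Section 2.3 fixes the cohort: "An initial safety and feasibility phase will include the first 50 study participants at each site". Section 2.3.1 adds: "The safety and feasibility phase will follow the same design as the full study, including 1:1 randomization, study drug administration, and counseling". It sets two reviews: one by site, with the two China sites probably taken together, and one across all 150 participants. The SDMC prepares the summaries for both.

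On adverse events, Section 2.3.2 says: "Management, reporting and review of adverse events and social harms will follow the procedures specified for the full study in Section 6.0". Under Section 6.2, events that are neither serious nor otherwise expedited are "recorded in the study source documentation but will not be included in the study database". The Appendix VI table agrees: non-serious events go into source documents but not onto the AE log.

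**The concern.** Section 7.3 applies a sample size of 50 to a limit on the rate for the intervention. The 50 at a site are split between two regimens, so only about half inform the rate on substitution. The text reports the chance of missing a 30% rate but does not discuss how often the same threshold is crossed when the rate is acceptable. Finally, the table deals with event rates of 10% to 30%. Rates that high would be expected mainly for ordinary clinical effects such as those listed in Section 8.3 (headache, nausea, sweating, constipation), and when these are non-serious the reporting rules keep them out of the database.

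The main purpose of this phase is to collect detailed safety data for the sponsor and for authorities in three countries. A reader who trusts the 4% would think the review more sensitive for the substitution regimen at a single site than it is, and could take an absence of tabulated events as reassurance.

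**Working it through.** **Inputs.** From the protocol: 50 per site and 1:1 allocation (2.3, 2.3.1); true rate 30% and acceptable maximum 20% (7.3); China sites likely combined and 150 at the second review (2.3.1). The implied threshold is an observed 20%, that is 10 of 50. Detoxification-arm rates and the share of events that are serious or expedited are not given; values for them below are assumptions.

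**Step 1. The plan's own figure.** With X ~ Bin(50, 0.30), P(X ≥ 10) = 0.9598, so the miss rate is 1 − 0.9598 = 4.02%. The stated 4% is reproduced. The other table cells also reproduce, except the last cell of the 10% row, which is 0.0245 and is printed as 0.03. That slip has no consequence.

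**Step 2. The substitution arm alone.** Keep the threshold at an observed 20% and set n to the number on substitution. Miss = 1 − P(X ≥ r | n, 0.30); false alarm = P(X ≥ r | n, 0.20).

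| Review unit | n on substitution | r | Miss at 30% | False alarm at 20% |
|---|---|---|---|---|
| Single site | 25 | 5 | 1 − 0.9095 = 9.0% | 57.9% |
| China sites combined | 50 | 10 | 4.0% | 55.6% |
| All sites (second review) | 75 | 15 | 1.9% | 54.6% |

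**Step 3. If a site's two arms are pooled.** The count is Bin(25, 0.30) + Bin(25, q), where q is the assumed detoxification-arm rate. Miss = P(sum < 10).

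| Assumed q | Expected events in 50 | Miss |
|---|---|---|
| 30% | 7.5 + 7.5 = 15 | 4.0% |
| 25% | 7.5 + 6.25 = 13.75 | 8.5% |
| 20% | 7.5 + 5 = 12.5 | 16.2% |
| 10% | 7.5 + 2.5 = 10 | 44.0% |

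At q = 10% the pooled rate is itself 20%, so a larger sample does not help: the miss rate is 46% for 50 + 50 (threshold 20) and 47% for 75 + 75 (threshold 30).

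**Step 4. What the threshold can show.** Ten of 50 is an observed 20%, the rate called acceptable; its exact 95% interval is 10.0% to 33.7%. The protocol's own 20% row gives P(X ≥ 10) = 0.56. A threshold crossed more often than not at an acceptable rate cannot support a conclusion that the rate is unacceptable.

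**Step 5. What reaches the database.** Section 2.3.2 sends the safety phase to Section 6.0. Section 6.2 and Appendix VI admit only serious and expedited events to the AE form. If a share s of a true 30% rate is admitted, the recorded rate is 0.30 × s. With n = 50 and threshold 10:

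| Assumed s | Recorded rate | Miss |
|---|---|---|
| 75% | 22.5% | 28.4% |
| 50% | 15% | 79.1% |
| 20% | 6% | 99.9% |

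The 20% limit therefore cannot be checked from databased adverse event records unless the term in Section 7.3 means only serious or expedited events, which it does not say.

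**The case against.** The defence has substance.

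- **Fifty is a reasonable cohort for early drug effects.** Both arms start BUP/NX on the day of randomisation (3.4) with similar induction (4.3.3), and detoxification can last up to 18 days of the four-week window. For an event equally common in both arms, the 4% is right. This stands.
- **Pooling is not stated.** A reader might infer it from the n = 50 table and from the word blinded in Section 2.3.1. That word is attached to the interim evaluation and not clearly to the site reviews, and Section 2.3.2 says the detoxification arm allows comparison with substitution. The 44% figure needs both pooling and an assumed 10% detoxification rate, so it is one end of a range and not an estimate.
- **The single-site figure is not the only one.** If the China data are combined, only Chiang Mai is left with about 25 on substitution at the first review. This stands.
- **Harms are not all hidden.** A reader might infer that a common harm would be invisible. Blood counts, creatinine, ALT and bilirubin are tested weekly (2.3.2), and the reviews cover laboratory data (2.3.1). That these results are databased separately is an assumption, but Section 6.2 does not exclude them. Section 6.1 leaves report content to the PSRT and SDMC, and Section 5.6 mentions case report forms for events reported at visits. Neither overrides the specific rule in Section 6.2 and Appendix VI for non-serious clinical events.
- **The example is an illustration, and the 0.56 is printed in the table.** True: no stopping rule is set, and concerns already go to the DSMB for unblinded review. The wording still presents the threshold as grounds for a conclusion, and the text discusses only the favourable error rate.

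**Conclusion.** The concern holds in a limited form. The 4% is correct for an event with the same rate in both arms that reaches the review. For the substitution regimen the miss rate at a true 30% is 9.0% at a single site, 4.0% with the China sites combined and 1.9% at the second review; these rest only on 1:1 allocation and a 20% threshold. The pooled range of 4% to 44% rests on an inference about pooling and on assumed detoxification rates of 30% to 10%. The 56% false-alarm probability is the protocol's own figure and needs no assumption.

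The firmest part is the conflict between Section 7.3 and the reporting rules: common non-serious clinical events would be absent from the adverse event data available for the SDMC summaries.

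The documents do not support saying that the evaluation cannot deliver its 4% at all, or that it is blind to harm. Nor is it a gate before full accrual, since Section 2.3.1 lets accrual continue during the site review. The point should be settled, but it does not undermine the trial's primary comparison.

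**What to change.** 1. **Data capture.** For the first 50 participants at each site, enter all graded adverse events through week 4 on the AE form, and amend Sections 2.3.2 and 6.2 and Appendix VI to match. The events and grades are already required in source. The cost is extra AE forms for about 150 participants (3 × 50) over four weeks, with no new visit or test. Section 4.4.1 mentions participants treated under version 1.0, so some may already be past week 4; for them the forms would be completed retrospectively from source.
2. **Section 7.3.** State the arm, sample size and event type to which the table applies. Give miss and false-alarm probabilities for the substitution arm at n = 25 (single site), 50 (China combined) and 75 (second review), as in the first table above. Describe the threshold as a trigger for the unblinded DSMB referral already in Section 2.3.1, and drop the wording about concluding harm. Correct the 0.03 cell to 0.02 in passing. The cost is one recomputed table and a few sentences.
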